### **7.9.2 Adverse Events**

Adverse events will be summarized by the number and percentage of subjects experiencing an event. Tables will show the overall incidence of AEs and the incidence for each treatment group. All reported AEs will be listed, but only TEAEs will be summarized.

#### **Adverse Events Counting Rules:**

1. A subject with more than one different AE in a particular system organ class (SOC) will be counted only once in the total of subjects experiencing adverse events in that particular SOC.
2. A subject having experienced the same event (AE preferred term) more than once during the study will be counted only once in the number of subjects with that event for counts of subjects or incidence measures.
3. If an event changes in intensity or in seriousness during the study, it will be counted only once with the worst grade and seriousness respectively.
4. If the causal relationship to the study drug is assessed differently, it will be counted only once by considering the “Worst” documented degree of relationship.

A TEAE overview summary table will be provided with the incidences of subjects with at least one TEAE, at least one serious TEAE, at least one TEAE related to study treatment, at least one serious TEAE related to study treatment, at least one TEAE leading to treatment discontinuation, at least one serious TEAE leading to treatment discontinuation, at least one TEAE leading to withdrawal from study, at least one serious TEAE leading to withdrawal from study, at least one severe TEAE, at least one severe study treatment-related TEAE, and number of deaths.

Summary tabulations of the following will be prepared for all subjects, for each treatment, for each primary system organ class, and for each preferred term within a system organ class. These will report counts and incidences of these categories:

- All TEAEs
- Study treatment-related TEAEs
- TEAEs leading to discontinuation of study treatment
- TEAEs leading to withdrawal from study
- Non-serious TEAEs with >5% incidence rate in any treatment group
- Serious TEAEs
- Study treatment-related serious TEAEs
- TEAEs by relationship to study treatment
- TEAEs by highest severity and treatment
- Severe TEAEs
- Severe study treatment-related TEAEs

Supporting data listings will be provided by treatment group, including:

- All AEs (including any AEs reported in the study)
- SAEs
- AEs resulting in study treatment discontinuation
- AEs leading to withdrawal from study

### **7.9.3      Laboratory Data**

Summary statistics (n, mean, median, SD, minimum, and maximum) for the baseline assessment and for the observed value and change from baseline at each nominal post-baseline visit for scheduled laboratory assessments of continuous laboratory variables will be tabulated. Shift tables (e.g., tables that show the number of subjects who are low, normal, or high at baseline vs. each post-baseline scheduled assessment) will be produced.

If there are multiple laboratory values for the same parameter at a given visit, the last value will be chosen for analysis.

All data will be displayed in subject data listings for Safety Analysis Set.

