In the ANB019-001 study in healthy adults, single doses of imsidolimab up to 750 mg administered by IV infusion or SC injection to 32 healthy adults in the SAD part of the Phase 1 study were generally well tolerated with a similar number of treatment-emergent adverse event (TEAEs) reported in subjects receiving imsidolimab or placebo, 29 subjects (81%) and 11 subjects (92%), respectively. The most frequently reported AEs were upper respiratory tract infection (URTI; 10 [28%] imsidolimab; 6 [50%] placebo), headache (10 [28%] imsidolimab; 3 [25%] placebo), and viral URTI (4 [11%] imsidolimab; 1 [8%] placebo). Additionally, multiple doses of imsidolimab up to 300 mg administered by IV infusion once weekly for 4 weeks to 18 healthy adults were also well tolerated. Overall, TEAEs occurred in 16 subjects (89%) receiving imsidolimab and in 3 subjects (50%) receiving the placebo. The most common AEs were headache (7 [39%] imsidolimab; 1 [17%] placebo) and URTI (3 [17%] imsidolimab; 1 [17%] placebo).

In ANB019-005, single doses of imsidolimab up to 750 mg administered by IV infusion or SC injection to 32 healthy Japanese and Caucasian adults were generally well tolerated. The most common TEAEs were alanine aminotransferase (ALT) increased (3 subjects [9.4%]) and aspartate aminotransferase (AST) increased (2 subjects [6.3%]).

One SAE of sepsis was reported in the ongoing ANB019-002 study in subjects with GPP; the SAE was considered possibly related to the study drug. The subject had a medical history of sepsis and experienced the SAE after the 750 mg IV dose administration. Antibiotic treatment rapidly resolved the sepsis episode with complete subject recovery. Further details of imsidolimab clinical studies are in the IB.

As allergic or anaphylactic reactions may occur in any subjects treated with mAbs, subjects should be observed during study drug administration and for a period of 2 hr after study drug administration. Subjects with true allergic/anaphylactic reactions should not receive further doses of the monoclonal antibody. Symptoms of an apparent allergic reaction to the drug, also known as ‘cytokine release syndrome’, vary dramatically but can include:

- Mild to moderate fever, chills, headache, nausea, and vomiting
- Moderate to severe symptoms such as edema, hypotension, and pulmonary infiltrates (eg, blood and mucus in the lung)

Efficacy and Safety of Imsidolimab in Subjects with Acne Vulgaris
Protocol ANB019-209

Version 1.0
11 February 2021

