During the COVID period, if any data is collected at a home visit, it will be recorded by the home nurse in the source documents and the originals will be sent back to the site for data entry into the electronic data capture system for storage/archiving.

- Clinical laboratory tests (chemistry and hematology) and pregnancy tests may be performed by local laboratory if home nursing visits are not possible and sample collection cannot be performed at the study site due to COVID 19-related limitations, including but not limited to site closure. Abnormal laboratory results should be promptly communicated to the Medical Monitor. Subjects' anonymity must be maintained when communicating results to the Medical Monitor.
- At home study drug administration by home health nurses may be done.
- Source documentation should note that the visit was performed virtually (not face-to-face), and note the name of the local laboratory where laboratory tests were done.
- If certain study procedures or assessments cannot be completed per the schedule of events, the reason for the missed assessment (ie, laboratory, vital signs, physical exams, etc.) must be noted in the source documentation (eg, COVID-19), captured in the protocol deviations documentation, and reported to the IRB/Ethics Committee, as applicable.

A detailed assessment of COVID-19 related risk and mitigation measures will be documented in the appropriate study plans.

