5.1 INCLUSION CRITERIA

To be eligible to participate in this study, a subject must meet all of the following criteria, either at the screening and Day 1 visits or only at one of the specified visits (screening or Day 1) as noted in the criterion:

1. Male and female aged 12 to 45 years (inclusive) at the time of signing the informed consent/assent.
2. Moderate to severe facial AV at Screening and Day 1, defined as follows:
 - a. Facial IGA score of 3 (moderate) or 4 (severe)
 - b. At least 20 and no more than 100 inflammatory lesions on the face
 - c. No more than 100 noninflammatory lesions on the face.
 - d. No more than 5 nodules (≥ 5 mm) on the face
3. Subject agrees to use Cetaphil Skin Cleanser on a regular basis (ideally once or twice daily) for at least 1 week prior to Day 1 and agrees to continue using Cetaphil Skin Cleanser at the same frequency throughout the study.
4. Subject must meet the following laboratory criteria at screening:
 - a. Hemoglobin ≥ 90 g/L (≥ 9 g/dL)
 - b. White blood cell count $\geq 3.0 \times 10^9$ /L ($\geq 3.0 \times 10^3$ / μ L)
 - c. Platelets $\geq 100 \times 10^9$ /L ($\geq 100 \times 10^3$ / μ L)
 - d. Serum creatinine < 132.6 μ mol/L (< 1.5 mg/dL)
 - e. Alanine aminotransferase (ALT) and aspartate aminotransferase (AST) ≤ 2 upper limit of normal (ULN)
 - f. Total bilirubin $\leq 1.5 \times$ ULN. Subjects with known Gilbert's disease who have serum bilirubin $< 3 \times$ ULN may be included
5. Body weight ≥ 40 kg and BMI within the range of 18 to 40 kg/m^2 for adults and 16 to 40 kg/m^2 for adolescents, inclusive { $\text{BMI} = \text{weight (kg)}/[\text{height (m)}]^2$ }.
6. Contraceptive use by men and women should be consistent with local regulations regarding the methods of contraception for those participating in clinical studies.
Contraception and pregnancy:
 - a. A male subject must agree to use contraception as detailed in [Appendix 1](#) of this protocol during the treatment period and for at least 200 days (which includes the duration of relevant exposure plus the duration of sperm cycle) after the last study treatment administration and refrain from donating sperm during this period.

- b. Female subjects:

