9.4.8.1 ADVERSE EVENTS AND SERIOUS ADVERSE EVENTS

A TEAE is defined as:

- A new event that occurs during or after first dose of study treatment or,
- Any event present at Baseline that worsens in either intensity or frequency after first dose of study treatment.

Adverse events will be coded using the MedDRA and only TEAEs will be summarized. Number of events and percentage will be tabulated by preferred term (PT) and primary system organ class (SOC). Multiple occurrences of an AE for a subject will only be counted once per primary SOC and PT. Percentages will be determined relative to the subjects in the safety analysis set for the given treatment arm.

If the intensity or seriousness of the AE changes, the overall intensity or seriousness will be the maximum intensity or seriousness of the multiple occurrences. The TEAEs, SAEs, TEAEs leading to treatment discontinuation, and TEAEs leading to withdrawal of subject will be tabulated for each treatment arm.

All AE data will be listed for each subject.

Summaries over SOC and PT of TEAEs, TEAEs leading to death, SAEs, and TEAEs that led to discontinuation from the study or study treatment will be presented by treatment. Summaries will also be presented by relatedness to the study treatment and the severity of the TEAE.

9.4.8.2 12-LEAD ELECTROCARDIOGRAM, VITAL SIGNS, AND CLINICAL SAFETY LABORATORY TESTS

Summaries and listings of data for vital signs and safety laboratory tests result (hematology, biochemistry, and urinalysis) will be presented. Appropriate descriptive statistics will be summarized for the observed value at each scheduled assessment and for the corresponding change from Baseline.

For hematology and biochemistry tests, listings of subject data will also flag any abnormal or out-of-range values. Clinically significant changes in the laboratory test parameters will be summarized and listed. Hematology and biochemistry data will be reported in System International units.

Descriptive statistics will be used to present the safety outcomes including, weight, BMI, 12-Lead ECG, vital signs, and clinical laboratory test results.

Change from Baseline will also be summarized for vital signs, and clinical laboratory tests results.

All ECG data results (normal/abnormal) will be summarized using frequency and percentage, and parameter values will be summarized descriptively. Clinically significant abnormalities will be presented in by-subject listings.

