#### **6.6.4      Laboratory Data**

Clinical laboratory tests that will be performed in this study are summarized in [Appendix 10](#) of the study Protocol. Local laboratory samples will be collected in the eCRF when the central laboratory results are not available immediately, and the Investigator needs to take an immediate decision for any safety concerns, however, local laboratory results will be not used in the summary tables. All laboratory data will be listed, but only hematology, biochemistry, and urinalysis will be summarized.

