#### Use of Data from Unscheduled Assessments for Laboratory, ECG, and Vital Sign Summaries (Continuous Parameters)

Data from unscheduled visits will be listed; duplicate unscheduled measurements will not be shown twice. If the data from the scheduled visit is missing, data from unscheduled visits that fall in the visit window of the same scheduled visit will be used. In cases where there are multiple unscheduled visits, the most recent unscheduled visit will be used.

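### The by-arm laboratory tables cannot count marked ALT, AST or bilirubin rises and can miss peaks outside scheduled central draws, and the protocol's summary of clinically significant changes is dropped without record

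*SAP*

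**What the plan says.** **Categories.** SAP 6.6.4 (Abnormal Values) classes each result as low, normal or high against the laboratory's range. SAP 7.9.3 then plans "Shift tables (e.g., tables that show the number of subjects who are low, normal, or high at baseline vs. each post-baseline scheduled assessment", together with n, mean, median, SD, minimum and maximum of the value and of its change at each nominal visit.

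**Selection of values.**
- Local results, SAP 6.6.4: "local laboratory results will be not used in the summary tables".
- Unscheduled results, SAP 7.1: "If the data from the scheduled visit is missing, data from unscheduled visits that fall in the visit window of the same scheduled visit" are used, and the most recent is taken if there are several. Otherwise they are only listed.
- Several values at one visit, SAP 7.9.3: the last is analysed.

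**Protocol context.**
- Section 4.5, COVID-19 fallback: "Clinical laboratory tests (chemistry and hematology) and pregnancy tests may be performed by local laboratory if home nursing visits are not possible" and the sample cannot be collected at the site.
- Section 8.2.6: clinically significant values are repeated until they settle. A local sample drawn for an urgent safety decision should be accompanied by a central one.
- Section 5.1, criterion 4: ALT and AST up to 2 x ULN and total bilirubin up to 1.5 x ULN are eligible, with a higher bilirubin bound for Gilbert's disease.
- Section 9.4.8.2: "Clinically significant changes in the laboratory test parameters will be summarized and listed".

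SAP 7.9.3 contains no such summary. SAP Section 8, which records changes from the protocol, lists only added exploratory analyses.

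**The concern.** Change in laboratory parameters is part of the secondary safety endpoint (Protocol 3.2). Protocol 2.3.1 reports ALT and AST increases as the most common TEAEs in one Phase 1 study. A reader of the study report will want to know how many subjects in each arm had a large transaminase or bilirubin rise. The planned laboratory tables do not answer that. Three range categories carry no size, every shift is tied to a scheduled visit rather than to the worst value, and the selection rules favour the scheduled or latest central result over a peak seen elsewhere. The one protocol display that would have summarised clinically significant changes has disappeared without being recorded as a change. What is at stake is the arm-level comparison of laboratory safety; no efficacy result is affected.

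**Working it through.** **1. The protocol's own figures.** Protocol 2.3.1 gives 3 and 2 subjects out of 32: 3/32 = 9.375% (stated 9.4%) and 2/32 = 6.25% (stated 6.3%). Both reproduce. If the ALT rate applied here (an assumption), an arm of 120/3 = 40 would have 40 x 3/32 = 3.75 such subjects. The exact 95% interval for 3/32 is 2.0% to 25.0%, or 0.8 to 10.0 subjects. These are reported increases of unstated severity, not marked rises.

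**2. The SAP categories applied to illustrative values (multiples of ULN, assumed).**

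| Baseline | Post-baseline | SAP cell |
|---|---|---|
| 0.5 | 1.1 | normal to high |
| 0.5 | 8 | normal to high |
| 1.5 | 1.6 | high to high, no shift |
| 1.5 | 8 | high to high, no shift |

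A rise from a normal baseline shows as a shift, but its size does not. A rise from an eligible high baseline shows as no shift at all.

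**3. The summary statistics.** Take 40 subjects, 39 at 0.5 x ULN and one at 8. The visit mean is (39 x 0.5 + 8)/40 = 0.69, against 0.50 without the rise. The maximum column shows 8, so a peak used as the scheduled-visit value is visible. The maximum is one number per arm and visit, however: one subject at 8 and several at 8 look the same, and ALT cannot be paired with bilirubin in the same subject.

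**4. Where a peak goes under the selection rules.**

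| Source of the peak | Laboratory tables |
|---|---|
| Scheduled central, sole value at the visit | Used |
| Scheduled central, with a later repeat recorded at the same visit | Replaced by the last value |
| Unscheduled central, scheduled value present | Not used |
| Unscheduled central, scheduled value missing | Used if in the window and the most recent |
| Local safety draw | Not used; a paired central value is expected, but may itself be unscheduled |
| Local replacing central under Protocol 4.5 | Not used; that section requires no paired central sample |

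**5. Chance that an excursion falls between draws.** Chemistry after Day 1 is drawn on Days 15, 29, 57, 85 and 141, giving gaps of 14, 14, 28, 28 and 56 days. Assume an excursion of L days starts with equal chance on any day from Day 2 and ends by Day 141, so there are 141 - L possible starts. Count the starts for which no nominal draw falls inside it.
- L = 7: 134 starts; draws catch 7 + 7 + 7 + 7 + 1 = 29; missed 105/134 = 78%.
- L = 14: 127 starts; draws catch 14 + 14 + 14 + 14 + 1 = 57; missed 70/127 = 55%.
- L = 28: 113 starts; draws catch 28 (Days 15 and 29 together) + 28 + 28 + 1 = 85; missed 28/113 = 25%.

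A missed excursion is known only if an unscheduled or local sample is taken. That value then goes to the listings and not to the laboratory tables, unless the scheduled value is missing and an unscheduled central value fills it.

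**6. Protocol against SAP.** Protocol 9.4.8.2 requires clinically significant laboratory changes to be both summarised and listed. SAP 7.9.3 gives visit statistics, range shifts and listings. The summary is missing, and Section 8 does not say so.

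**The case against.** The strongest reply is that a marked rise has several ways of being seen, and most of it stands. The maximum column shows a peak that is used for a scheduled visit. Protocol 8.2.1.1.1 makes a laboratory abnormality an AE when the investigator judges it clinically significant, whether the sample was central or local, scheduled or not, and SAP 7.9.2 tabulates TEAEs by arm and preferred term. All laboratory data are listed and out-of-range values flagged. Local safety draws should have a central pair. The COVID-19 route needs both home nursing and site collection to be unavailable, and its frequency is unknown. The repeat rule starts from a value already found significant, which may be a scheduled central value that SAP 7.1 keeps. The shift-table wording is only an example, and the mock tables are in a separate document not available here.

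A reader might therefore be tempted to conclude that a marked rise can vanish from every table, or that the tables leave out the worst values by construction. The documents support neither: complete absence needs a value that is off-schedule, local or replaced and that is also not reported as an AE. Nor are ALT and AST the single risk the protocol names. Section 2.3.1 also covers gastrointestinal infection, sepsis and allergic reactions, and gives no severity for the liver enzyme events.

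The other routes do not replace the missing display. Entry to the TEAE tables depends on investigator judgement, Protocol 8.2.1.4 prefers the diagnosis to the abnormal test as the reported term, and AE severity (8.2.1.3.1) is not defined by laboratory magnitude. Listings give no comparison by arm.

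**Conclusion.** The point holds in a limited form. Under the stated rules, the by-arm laboratory tables cannot count marked ALT, AST or bilirubin rises, and they can miss a peak seen only at an unscheduled or local draw or replaced by a later repeat. The unrecorded loss of the protocol's summary of clinically significant changes stands without any assumption.

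The high-to-high problem applies only to subjects already above ULN at baseline, whose number is unknown. The 78%, 55% and 25% figures depend on the assumed durations, uniform onset and nominal visit days; they describe gaps in the schedule and do not estimate how many peaks would be lost. A reader might infer that laboratory safety would be reported as clean when it is not. The documents do not show that, because such values stay in the listings, in the visit maximum if used, and in the TEAE tables if judged significant. This is a change worth making to the safety displays. It does not touch the primary analysis, alpha or sample size.

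**What to change.** - **SAP 7.9.3:** add a by-arm table of the worst post-baseline value over all scheduled, unscheduled and local results. Express ALT, AST and bilirubin as multiples of the reporting laboratory's own ULN, with reporting categories chosen by the sponsor before unblinding, cross-tabulated by baseline multiple (at or below 1 versus above 1 x ULN). SAP 7.9.5 already uses the worst post-baseline value for ECG, although its three categories carry no magnitude either.
- **SAP 6.6.4:** where a local result is the only one for a visit, use it in the tables, normalised to its own reference range.
- **SAP 7.9.3:** restore the protocol's summary of clinically significant laboratory changes.

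The cost is SAP wording, one or two more tables from results already collected, and capture of local reference ranges so that multiples of ULN can be calculated.

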### **7.9.4      Vital Signs**

Summary statistics (n, mean, median, SD, minimum, and maximum) of the raw values and change from baseline for pulse rate, systolic blood pressure, diastolic blood pressure, body temperature, respiratory rate, weight, and height will be tabulated by treatment and visit separately for adolescents and adults, as well as together.

Vital sign measurements (pulse rate, systolic blood pressure, diastolic blood pressure, body temperature, respiratory rate, weight, and height) during the study will be displayed in a vital signs listing.

### **7.9.5      Electrocardiogram (ECG)**

ECG data (heart rate, PR interval, RR interval, QRS interval, QT interval, and QTcF interval) will be tabulated with summary statistics (n, mean, median, SD, minimum, and maximum) by visit for both the raw values as well as the changes from baseline. If there are multiple ECG values for the same parameter at a given visit, the last value will be chosen for analysis.

The overall ECG results will be classified by the investigator as “normal,” “abnormal, not clinically significant,” or “abnormal, clinically significant.” Three-by-three contingency tables will be presented to summarize the shift from the baseline category to the worst post-baseline value. Summary results will include the count and percentage of subjects within each shift category and treatment group.

All ECG data as well as clinically significant abnormalities will be presented in a by-subject listing.

### **7.9.6      Other Safety Assessments**

Chest X-ray, physical examination, TB test results, pregnancy test, viral serology, and FSH will be presented in listings for the Safety Analysis Set. The overall evaluation of physical examination results at each visit will be listed for subjects with any abnormal physical examination findings. No AEs of special interest will be defined.

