2.3 RISK/BENEFIT ASSESSMENT

2.3.1 KNOWN POTENTIAL RISKS

No major toxicities were observed in the 4-week repeat-dose toxicity study in cynomolgus monkeys. The main finding consisted of minor, injection site reactions associated with the SC route of administration and not considered AEs.

In cynomolgus monkeys, treatment-related effects observed in the 13-week repeat-dose toxicity study included protozoa in the stomach, an increase in nonformed feces and prolapsed rectum observations; the latter observation was not considered dose related. The increase in protozoa in the stomach has been observed in monkeys treated with immune-modulating drugs (Dubey 2002) and is consistent with the putative mechanism of action of imsidolimab. During the 26-week repeat-dose toxicity study, imsidolimab-related effects were limited to a low incidence of liquid feces. In the monkeys, the increased incidence of protozoa, nonformed feces, and prolapsed rectum were not considered AEs as they responded to veterinarian intervention. In humans, gastrointestinal infections can be clinically monitored and, in the case of most protozoa, are readily treatable even in the context of immunocompromised individuals (Farthing 2006).

One female monkey receiving 60 mg/kg imsidolimab IV was found moribund on Study Day 34. The cause of death was not determined and had an uncertain relationship to imsidolimab but

Efficacy and Safety of Imsidolimab in Subjects with Acne Vulgaris
Protocol ANB019-209Version 1.0
11 February 2021

could be due to treatment-related immune modulation. However, data published on IL-36R deficient humans shows no deleterious effect on general health, and normal immune function is broadly preserved, indicating that inhibition of IL-36R, does not generally compromise host defenses. Similar to other immune-modulating treatment paradigms, subjects should be closely monitored for any clinical gastrointestinal manifestations including infections and evaluated on an ongoing basis. If a gastrointestinal infection is suspected, the subject should be treated as clinically indicated.

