## 7.9 Safety Analyses

Safety analyses will be performed using the Safety Analysis Set. Safety parameters include AEs, exposure, clinical laboratory parameters (hematology, biochemistry, and urinalysis), vital signs, and ECGs. Summaries of safety parameters will be presented overall as well as by treatment group.

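### Cheap improvement: no planned table counts subjects with at least one gastrointestinal event or at least one allergic event, the two multi-term harms Protocol 2.3.1 singles out

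*SAP*

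**What the plan says.** **The harms named.** Protocol 2.3.1 reports that treatment-related effects in the 13-week monkey study "included protozoa in the stomach, an increase in nonformed feces and prolapsed rectum observations", and links the protozoa to the presumed mechanism of action. It then says that "subjects should be closely monitored for any clinical gastrointestinal manifestations including infections". Separately it warns: "As allergic or anaphylactic reactions may occur in any subjects treated with mAbs". The symptoms it lists for such reactions run from fever, chills, headache, nausea and vomiting to edema, hypotension and pulmonary infiltrates.

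**The analysis planned.** SAP 7.9.6 states: "No AEs of special interest will be defined". SAP 7.9.2 has an overview table (any TEAE, serious, related, severe, leading to discontinuation, and so on). Its detailed tables are then laid out "for each primary system organ class, and for each preferred term within a system organ class". Cuts by relationship, severity and seriousness use the same rows. Under the counting rules, a subject with several different events in one SOC is "counted only once in the total of subjects experiencing adverse events in that particular SOC". Protocol 9.4.8.1 has the same scheme: "Multiple occurrences of an AE for a subject will only be counted once per primary SOC and PT". On columns, SAP 7.9 says: "Summaries of safety parameters will be presented overall as well as by treatment group".

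Neither document contains a term list, standardised query or composite for either harm. Table mock-ups are in a separate document (SAP Appendix 3) that is not available here.

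**The concern.** Each harm is a clinical concept, not a single coded term. The protocol's gastrointestinal concept explicitly takes in infections, so its events can be expected to fall in at least two SOCs, one for gastrointestinal disorders and one for infections. Each of those would also hold events that have nothing to do with the concept, such as upper respiratory infections in the second. Allergic presentations recorded as symptoms could spread further. (Which term sits in which SOC is a MedDRA matter that the documents do not set out, so this placement is an assumption.)

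Counting once per SOC removes duplicates within a class but not across classes. A reader of the planned tables who asks how many subjects in each arm had any enteric event, or any allergic reaction, will not find the answer. It could be assembled from the listings, but the terms would then be chosen after treatment results are known, which is what pre-specification is meant to avoid.

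**Working it through.** **Inputs.** About 120 subjects randomised 1:1:1 (SAP 3.5): 120 / 3 = 40 per arm, and 2 × 40 = 80 on imsidolimab, taking all randomised subjects as dosed. The plan gives no expected rate for either harm, so there is no figure of its own to reproduce and every risk below is an assumption.

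**1. Can the count be rebuilt from the rows?** If a subjects appear in one SOC row and b in another, the number with at least one event lies between max(a, b) and a + b. Take the cleanest case, where both rows hold only relevant events:
- a = 2, b = 2: 2 to 4 of 40, or 5% to 10%
- a = 4, b = 2: 4 to 6 of 40, or 10% to 15%
- a = 4, b = 4: 4 to 8 of 40, or 10% to 20%

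The rows bound the rate but do not give it. Unrelated events in the same SOC loosen even the bound, and PT rows overlap across subjects in the same way.

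**2. Can a pooled imsidolimab figure be rebuilt?** For any single row, yes. Each subject belongs to one arm, so the two active columns can be added and divided by 80. Only the count across rows is missing.

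**3. How much does scatter hide?** SAP 7.9 plans no tests on adverse events, so this measures how visible a signal would be; it is not the power of a planned analysis. Assume true per-subject risks of 20% on imsidolimab and 5% on placebo, arising from m independent, equally likely terms or classes. The risk per row is 1 − (1 − p)^(1/m).
- m = 4 (PT rows): 1 − 0.80^(1/4) = 5.4% v 1 − 0.95^(1/4) = 1.3%
- m = 2 (SOC rows): 1 − 0.80^(1/2) = 10.6% v 1 − 0.95^(1/2) = 2.5%

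The chance of flagging is the summed binomial probability of all outcomes with the higher rate on imsidolimab and a two-sided Fisher p ≤ 0.10. For at least one of m independent rows it is 1 − (1 − π)^m, where π is the chance for one row.

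| 20% v 5%, 80 v 40 | Chance flagged |
|---|---|
| One grouped count | 0.704 |
| Any of four PT rows: 1 − (1 − 0.089)^4 | 0.31 |
| One given SOC row of two | 0.403 |
| Either SOC row: 1 − (1 − 0.403)^2 | 0.64 |

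The SOC figures assume no unrelated events in those rows; background events would lower them. The any-row figures also give several unadjusted chances of a false flag.

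Other assumed risks, 80 v 40:
- 25% v 5%: grouped 0.887; any of four PT rows 1 − (1 − 0.207)^4 = 0.60
- 15% v 5%: grouped 0.439; any of four PT rows 1 − (1 − 0.025)^4 = 0.10

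For one arm against placebo (40 v 40) at 20% v 5%, the grouped figure is 0.54 and any of four PT rows gives 1 − (1 − 0.040)^4 = 0.15.

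**4. What would the grouped row look like?** Exact 90% intervals at an observed 10%: 4/40 gives 3.5% to 21.4%; 8/80 gives 5.1% to 17.3%.

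**The case against.** The strongest reply is that this is a legitimate choice. Protocol 9.4.8.1 plans SOC and PT summaries only and asks for no events of special interest; the SAP follows it. The instruction to monitor closely concerns care during the trial, not analysis. The all-TEAE table has no frequency cut-off and every event is listed, so nothing is lost. Protocol 8.2.1.5 asks for the diagnosis, where possible, rather than individual signs and symptoms, so a recognised allergic reaction or gastroenteritis should be one term. The protocol also says the monkey gastrointestinal findings were not considered adverse events, and that the 26-week effects were limited to a low incidence of liquid feces. All of this stands. It makes the point an improvement and reduces the expected scatter, but it does not supply the missing count.

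Three stronger readings might tempt a reader, and the documents do not support them:
- *That no column gives the rate on imsidolimab.* Each regimen has its own column, and the two can be added row by row. The overall column does mix 80 active with 40 placebo subjects, but that misleads only someone who sets it against placebo and ignores the arm columns.
- *That the safety objective goes unanswered.* The endpoint in Protocol 3.2 is the incidence of AEs, SAEs and AEs leading to discontinuation, with laboratory, vital-sign and ECG changes. The plan reports these.
- *That upper respiratory infection swamps the infection class because it was the most frequent Phase 1 event.* Protocol 2.3.1 shows headache level with it after single doses in ANB019-001 (10 subjects each on imsidolimab) and ahead after multiple doses (7 v 3). In ANB019-005 the most common event was raised ALT.

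It would also be unfair to set the pooled grouped 70% beside the 9% for one named PT row, or the 4% for one row in one arm. That mixes the effect of grouping with those of naming a row in advance and of pooling the arms.

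**Conclusion.** The point holds as a cheap improvement, not an error or a contradiction between the documents. What is certain is structural: no analysis described in the protocol or SAP counts subjects with at least one gastrointestinal (including infectious) event or at least one allergic reaction, and the planned rows only bound that count.

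The size is illustrative. Under the assumed 20% v 5%, grouping raises visibility from 31% (any of four PT rows) to 70%. Against SOC rows the gain is from 40% for one given row, but only from 64% if either of two undiluted rows is allowed to raise the flag. The case therefore rests more on having a defined, de-duplicated count chosen under blind than on any gain in power. The figures depend on invented risks, an equal split and independent terms; diagnosis-level recording would shrink the differences. The unseen mock-ups might add something, though the sentence in SAP 7.9.6 suggests not.

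**What to change.** Replace the sentence in SAP 7.9.6 and add to SAP 7.9.2 two pre-specified term groupings: (1) gastrointestinal infection or diarrhoeal event; (2) hypersensitivity or anaphylactic reaction. Define each by a term list fixed under blind. SAP 3.4 unblinds the primary analysis once all subjects have reached Week 12 or discontinued, while the blinded data review meeting in SAP 7.3 is tied only to final database lock. The lists should therefore be fixed when the SAP is finalised, before the primary-analysis snapshot.

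Report n (%) of subjects with at least one event per grouping, for each arm and for all imsidolimab combined, with the difference from placebo and a 90% CI (the level Protocol 9.4.1 already uses), labelled descriptive. Groupings for serious infection including sepsis, and for injection-site reactions, are optional, since no scatter has been shown for them.

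The cost is SAP wording, two term lists, one table and one listing from data already collected. The downside is a little programming and a few unadjusted descriptive comparisons. Nothing in data collection or clinical management changes.
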